# **Healthcare Effectiveness Data & Information Set (HEDIS)**

HEDIS scores are a standard system to measure patients' compliance to health care treatment/testing for a variety of conditions/diseases. A retinol eye examine is part of the diabetes HEDIS score, and this is included with our exam. We would like to review the diabetic HEDIS scores at Hamilton Clinic through their database to see if there have been changes following the implementation of the SIGHT program. This database is de-identified.

Recording of Data: The ophthalmic technicians will enter all data from each patient encounter into both the UM EHR. The research assistant will then enter the data from the EHR into a secure research database, REDCap. Data will be entered into the EHR as a nocharge research visit. The ophthalmologist's letter to the patient with the diagnosis and plan will be abstracted from the EHR by the Project Manager and the diagnosis and follow-up plan will be entered into REDCap. The Project Manager will also run weekly reports from the EHR to assess adherence to follow-up recommendations for study participants and enter this data into REDCap.

#### **Visual Impairment**

We will review participants with visual impairment of Best Corrected Visual Acuity (BCVA) less than 20/70 or legally blind BCVA 20/200 or worse in the better seeing eye and visual field results with less than 20 degrees in the better seeing eye. We will determine if there is any statistical significance between presence of visual impairment and demographic data. Additionally, we will determine the proportion that meet the requirements for Michigan Bureau of Services for Blind Persons for participants with progressive and non-progressive disease.

# Pupillary Light Reflex Device Data Collection- Completed 10/2023

The pupillary light reflex (PLR) is a standard part of every eye examination used by eye care professionals to provide critical information about the health and integrity of the visual system. When light is directed at the pupil, stimulated photoreceptors in the retina transmit the signal through the optic nerve to the midbrain. The sensory signal is processed in the midbrain and the autonomic nervous system via the parasympathetic (pupil constriction) and sympathetic (pupil dilation) nerves, coordinating a motor response in both the stimulated and unstimulated eye. However, the typical PLR relies on subjective observation by examiners and the data collected is imprecise. Consequently, current PLR assessment suffers from poor reliability and reproducibility, affecting its utility across care settings over time.

To address these issues, we have developed an inexpensive, binocular, handheld PLR system that captures high resolution video imaging and determines pupil constriction dynamics with machine vision algorithms. The quantitative PLR system (Q-PLR) is a handheld binocular device requiring minimal operator effort and skill that uses machine vision algorithms to capture high resolution video images and information about pupil constriction dynamics. Using LED light sources and low-light infra-red cameras, the Q-PLR automatically tracks pupils, and captures static and dynamic pupillary parameters. Pupillary measurements are accurate to 0.5mm, or less, and sampled at 30 frames per second, which is an appropriate sampling frequency to assess pupillary changes. Unlike the pupillometers currently available for clinical use, both pupils are imaged, measured, and recorded simultaneously. Assessment of inter-pupillary responses provides additional information about the relative integrity of retinal and optic nerve function. While preclinical testing of the prototype system has been reproducible, further testing in real-world clinical settings must be performed to assess the robustness of the system. First, further testing in real-world clinical settings must be performed to assess the accuracy, reliability, and robustness of the system to environmental and operator variability when compared to standard pupil exams. Second, the system must demonstrate clinical usefulness for clinicians and paraprofessionals using the device. To accomplish these aims, we will collect clinical examination data captured as part of the standard eye examination from participants in the SIGHT program and compare to Q-PLR image capture. We will additionally obtain qualitative feedback from ophthalmic technicians to improve device usability. We will only ask English and Spanish speaking participants to take part with this measurement. Data collected from the Q-PLR will not be reviewed for participant assessment. There is no known risk, the device camera operates like a smart phone.

#### **Outcomes**

Primary: The primary outcomes will be the number of participants screened and the prevalence of glaucoma/glaucoma suspect diagnosis and the cost per case of detected disease.

Secondary: 1a) Prevalence of other eye disease: visual impairment (visual acuity in the better seeing eye <20/40) on screening presentation, refractive error, cataract, diabetic retinopathy, and age-related macular degeneration. Prevalence will be determined by dividing the number of cases of disease on initial screening exam by the total number of participants who received screening each year. 1b) Incident disease will be estimated by

assessing the number of new cases of eye disease among the participants screened in the first year who returned for repeat screening in the third year. 2) The mean time since last eye exam: will be reported for the entire cohort of new patients seen for screening. The proportion of patients whose last eye exam was >2 years prior will be calculated for the cohort. 3) Vision related quality of life (NEI VFQ 9) will be assessed for all participants. The associations of vision related quality of life with eye disease diagnosis and demographic variables will be assessed. The 2-year change in vision and vision related quality of life will be measured for all participants screened in the first year of the program and re-screened in Year 3.

Sample Size: Approximately 5,000 patients access the Hope Clinic per year and 25,000 patients access the Hamilton clinic per year. One technician will be assigned full-time to Hamilton. The other technician will split time between Hope (60%, Tuesday, Wednesday, Thursday) and Hamilton (40%, Monday and Friday) because there is such a higher volume of patients to screen at Hamilton and the Hope Clinic is not open on Mondays or Fridays. The clinic equipment at Hamilton will be set up to be used by both technicians. A typical day for each technician will include 5 screenings and 5 one-month follow-up visits. In the first 2 years (48 weeks each) at each site, all screenings will be of new or 1 year follow up patients. In the 3rd year, 2 will be new and 3 will be one or two-year re-screening visits. At Hope, the technician has capacity for 2448 new screenings and 432 repeat screenings in 4 years. At Hamilton, the technicians have capacity for 4872 new screenings and 1008 rescreenings in 3.5 years. Thus full capacity is 7320 new screenings and 1440 re-screenings. Operating at just 80% capacity enrolls over 5,800 patients for new screenings including over 1100 with 2-year re-screenings to determine impact on longer term visual acuity and visual function.

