#### SPECIFIC AIM/HYPOTHESIS

Aim 1: (Phase 1- HUM 00173023) Use community-engaged research strategies to overcome key logistical and psychosocial barriers to accessing glaucoma care for uninsured and underinsured adults. To engage communities in glaucoma program development, we will create a Community Advisory Board (CAB) to solidify a trusting partnership between the University of Michigan, the Hope Clinic, Hamilton Community Health Network. We will conduct semi-structured interviews with patients and community stakeholders to understand barriers to eye care and inform program development and implementation.

Aim 2: (Phase 2- HUM 00169371) Develop a sustainable telemedicine model for glaucoma screening and care in community clinics. We hypothesize that a validated Veteran's Affairs (VA) telemedicine glaucoma screening program will identify a higher prevalence of glaucoma in primary care community clinics than screening the general population. We will test this hypothesis by implementing: (1) an automated technician-lead glaucoma screening with the VA protocol in the Hope and Hamilton partner community clinics for approximately 5,800 participants over 4 years; (2) remote ophthalmologists' grading of glaucoma screening tests for diagnosis and management; (3) a one-month follow-up visit with the technician to deliver low-cost eyeglasses and to educate and arrange ophthalmology care for participants who screen positive for eye disease; and (4) assess a 24-month change in vision and vision-related quality of life among participants screened during Year 1.

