has moderate or severe glaucoma, they can be referred to see the glaucoma specialist from UM who will have one day of clinic per month at Hamilton Clinic. If a patient from Hope requires further specialty consultation or surgery, they will sign up for MSupport, the UM charity care program, with the financial counselor available on-site during the Saturday clinics. Once a patient receives MSupport, they receive free care and medications at the UM for 12 months with the option to renew the services annually with proof of low income. Once a patient receives MSupport, they will be scheduled with the appropriate provider at the UM. For participants that are glaucoma/glaucoma suspect and seen at Hamilton or the Kellogg Eye Center for their follow up exam, these findings and visual field data will be collected and entered into the REDCap database.

One-Year Vision Outcomes: Repeat screenings at one year following the participants initial enrollment will take place during the second and third year of the program, where phone calls will be made to participants screened in the first or second year of the program (regardless if they screened positive or negative for disease) to encourage them to return for a second screening. When they return, they will follow the same protocol as described for the initial visits with the ophthalmic technician above. Although, One-Year visit survey data will only include demographics and the VFQ-9 and Falls survey which they also completed in their initial enrollment. Participants who were already randomized to the clinical trial in Aim 3 will not be re-randomized.

**Two-Year Vision Outcomes**: Repeat screenings will take place during the third year of the program, where phone calls will be made to all participants screened in the first year (regardless if they screened positive or negative for disease) to encourage them to return for a second screening. When they return, they will follow the same protocol as described for the initial visits with the ophthalmic technician above. Participants who were already randomized to the clinical trial in Aim 3 will not be re-randomized.

Participants that do not return to the clinic for a repeat screening examination, will be asked to complete the VFQ-9 survey over the phone when they are contacted.

One and Two-Year Vision Outcomes: These participants will need to meet the inclusion/exclusion criteria listed in section Recruitment Section of this protocol.

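### The 24-month change in vision and VFQ-9 is defined and scheduled by programme year, so individual intervals of 12 to 36 months qualify

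*Protocol*

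**What the plan says.** Under Specific Aim/Hypothesis, Aim 2 undertakes to "assess a 24-month change in vision and vision-related quality of life among participants screened during Year 1". No window is attached to the 24 months.

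The Aim 2 Outcomes section, secondary item 3, measures the two-year change in "participants screened in the first year of the program and re-screened in Year 3". Item 1b estimates incident disease from the new cases found in that same Year 1 cohort on its return in Year 3. It gives no person-time denominator.

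The Two-Year Vision Outcomes paragraph sets the scheduling rule: "Repeat screenings will take place during the third year of the program". Calls go to everyone in the Year 1 cohort. Participants who do not come back are asked for the VFQ-9 by phone whenever they are reached.

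The One-Year Vision Outcomes paragraph is worded differently: "Repeat screenings at one year following the participants initial enrollment will take place during the second and third year of the program". That visit is tied to the participant's own enrolment.

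The Sample Size section gives Year 3 three re-screening slots per technician day, shared between one-year and two-year visits. It describes the resulting total at 80% capacity, over 1,100, as two-year re-screenings.

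**The concern.** The aim names an interval, while the outcome definition and the scheduling rule name two calendar blocks, each a year wide. Two blocks of that width do not fix an interval. Change in acuity, change in VFQ-9 and the number of new cases all depend on elapsed time, so a result labelled 24 months could pool people observed for one year with people observed for three. A reader could not tell how much of the change or incidence belongs to two years.

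One-year and two-year visits also share Year 3, and no rule says which is which. A visit can therefore enter the two-year result although it was made in response to the one-year call.

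**Working it through.** **Inputs.** Programme Year 1 is months 0 to 12 and Year 3 is months 24 to 36 (Outcomes; Two-Year Vision Outcomes). From Sample Size: 48 working weeks a year, 5 screenings per technician day, Hope 3 days a week, Hamilton 7 technician-days a week (5 + 2), and in Year 3 a daily split of 2 new and 3 repeat.

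**1. The plan's own figures.**
- Hope: 3 × 48 = 144 days a year. New: 720 + 720 + 288 + 720 = 2,448. Repeat: 3 × 144 = 432.
- Hamilton: 7 × 48 = 336 days a year. New: 2.5 × 1,680 + 2 × 336 = 4,872. Repeat: 3 × 336 = 1,008.
- Totals: 7,320 new and 1,440 repeat. At 80%: 5,856 and 1,152, which agrees with the stated figures of over 5,800 and over 1,100.

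The totals reproduce only if all counted repeat slots sit in Year 3. Those 1,440 slots are shared by one- and two-year visits.

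**2. Bounds on the interval.** Let E be the enrolment month (0 to 12) and S the re-screening month (24 to 36). Then D = S − E has minimum 24 − 12 = 12 and maximum 36 − 0 = 36 months. If the 48-week years ran back to back, the range would be 48 to 144 weeks, about 11 to 33 months; the point is unchanged.

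**3. Late one-year visit.** A Year 1 enrollee's one-year date is E + 12, in months 12 to 24. Someone enrolled at month 11 is due at month 23. Returning at month 25, the person has D = 14 months, yet was screened in Year 1 and re-screened in Year 3.

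**4. Spread.** The documents do not give the recall order, so two cases bracket it.
- Recall in enrolment order at a similar pace: D stays near 24 and the spread is small.
- E and S uniform and independent (assumption): D is triangular on 12 to 36. Mean = 30 − 6 = 24. SD = √(12²/12 + 12²/12) = √24 ≈ 4.9 months. P(|D − 24| > w) = (1 − w/12)², so for w = 6 it is 0.5² = 25%, half below 18 months and half above 30. The central 95% is 14.7 to 33.3 months. A simulation of 1,000,000 draws agreed.

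**5. Incidence, for illustration.** Assume 10% cumulative incidence at 24 months and a constant hazard. At m months it is 1 − 0.9^(m/24): 5.1% at 12 months and 14.6% at 36.

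**6. Can the visit be anchored?** The participant's own 24-month date is E + 24, which runs from 24 to 36 and so always falls in Year 3. A strict ±3-month window runs from E + 21 to E + 27. It opens in Year 2 when E < 3 and closes in Year 4 when E > 9. The capacity totals in step 1 hold no two-year slots in either year.

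**The case against.** The best defence is that the Year 1/Year 3 wording only says which cohort returns and in which programme year. The interval itself is called 24 months or two years in the aim, in the Two-Year Vision Outcomes label and in the outcome item, and every 24-month date does fall in Year 3. What is absent is then a tolerance, which a SAP or visit manual commonly supplies. Sample Size also speaks of re-screens as one-year or two-year, so a visit at 12 months would naturally be called a one-year visit.

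Part of this stands. The programme-year wording is compatible with a 24-month target, and a SAP not shown could add a window or adjust for elapsed time. But a SAP does not schedule visits. The protocol states a recall rule, and that rule lacks the individual anchor that it gives the one-year visit a paragraph earlier. Nor does it say how a Year 3 visit is to be typed.

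A reader might infer more than the documents support:
- That most two-year visits will be badly off target. Under independence 56% would lie more than 3 months from 24 (0.75² = 0.5625), but no text supports independence over recall in enrolment order.
- That the average two-year change is biased. Under even spread the mean interval is still 24 months, and change roughly linear in time would leave the average unmoved. Bias needs return time to depend on disease, vision or reachability. The idea that hard-to-reach participants have longer intervals is plausible but has no basis in the text.
- That item 1b claims a two-year incidence. It does not use that term; it shares the cohort and therefore the interval.

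**Conclusion.** The point holds as a badly fixed definition. The protocol promises a 24-month change but defines and schedules it so that any interval from 12 to 36 months qualifies, including a late one-year visit made in Year 3; item 1b inherits the same interval. The bounds follow from the wording alone. The spread within them is not known: it ranges from small, under ordered recall, to an SD of about 4.9 months under uniform independent dates. The definite harm is mislabelling and mixed exposure time; bias in the mean change is possible but not shown. The outcomes are secondary, and neither the Aim 2 primary outcomes nor the randomised Aim 3 comparison depends on them, so the weight is minor to moderate.

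**What to change.** In Two-Year Vision Outcomes, time the recall call, and the phone VFQ-9 for those who do not return, to each participant's own 24-month date. In practice this is a recall list sorted by enrolment date, with no two-year slots needed outside Year 3.

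In the Aim 2 Outcomes section:
- classify each re-screen as one-year or two-year by actual elapsed time from baseline, with a stated cut (for example the 18-month midpoint);
- report the distribution of intervals;
- account for elapsed time in the analysis of change in vision and VFQ-9;
- express 1b as new cases per person-year among those free of the disease at baseline.

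A narrow ±3-month exclusion window is not advised. It spills into Years 2 and 4, where no two-year capacity is counted, and would discard usable visits in a study that reports about 35% no-shows and last-minute cancellations.

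The cost is a little more scheduling and analysis work plus the protocol wording. If the Year 3 recall is already over, the analysis part still applies, since encounters are entered in the health record and REDCap and the intervals can be computed from the visit dates.

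### The Aim 2 capacity figures at 80% use leave no slots, beyond rounding, for the one-year re-screens that the protocol places in the same slots

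*Protocol*

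**What the plan says.** The Sample Size paragraph (Protocol, Aim 2, under Outcomes) builds capacity from technician-days, five screenings per day and 48-week years. It describes the use of the slots as follows:

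- Years 1 and 2: "all screenings will be of new or 1 year follow up patients".
- Year 3, per technician-day: "2 will be new and 3 will be one or two-year re-screening visits".
- Total: "Thus full capacity is 7320 new screenings and 1440 re-screenings".
- Planning statement: "Operating at just 80% capacity enrolls over 5,800 patients for new screenings including over 1100 with 2-year re-screenings".

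The One-Year Vision Outcomes paragraph adds: "Repeat screenings at one year following the participants initial enrollment will take place during the second and third year of the program". It says that "phone calls will be made to participants screened in the first or second year of the program", whether or not they screened positive. On visit content it says: "When they return, they will follow the same protocol as described for the initial visits with the ophthalmic technician above", with a shorter set of surveys. For the two-year visit in Year 3, "phone calls will be made to all participants screened in the first year".

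The figure of 5,800 recurs as the approximate enrolment in Specific Aim 2 and as the n behind the margin of error in the Aim 2 Data Analysis.

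**The concern.** The words and the numbers of the Sample Size paragraph do not describe the same allocation. In words, one-year re-screens share the slots with new patients in Years 1-2 and with two-year visits in Year 3. In numbers, the Year 1-2 slots are all new, and the closing clause treats the Year 3 repeat slots as all two-year.

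Two planning figures depend on this. The number of participants screened is itself a primary outcome of Aim 2, and 5,800 is its target. The figure of over 1,100 is the only size given for the two-year cohort, which supports the secondary outcomes of incident disease and two-year change in vision and in quality of life. The quality-of-life questionnaire can be completed by phone by people who do not return. The other two need a repeat examination, so the slot count bears mainly on them.

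**Working it through.** **Inputs (Sample Size paragraph).** Five screenings per technician-day; 48 weeks per year. Hope has 3 technician-days per week over 4 years. Hamilton has 5 + 2 = 7 technician-days per week over 3.5 years. In Year 3 each day has 2 new and 3 repeat screenings.

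**Step 1. Reproduce the stated capacity, taking every slot outside the Year 3 repeat block as new.**
- Hope new: 3 × 48 × (5 + 5 + 2 + 5) = 2,448. Hope repeat: 3 × 48 × 3 = 432.
- Hamilton new: 7 × 48 × (5 + 5 + 2 + 2.5) = 4,872. Hamilton repeat: 7 × 48 × 3 = 1,008.
- Totals: 7,320 new and 1,440 repeat, 8,760 slots in all.

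All six figures match the protocol. The match requires the full 5 per day in Years 1 and 2 to be new patients.

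**Step 2. Apply 80% use.** 0.8 × 7,320 = 5,856 (stated as over 5,800). 0.8 × 1,440 = 1,152 (stated as over 1,100). Together these are 0.8 × 8,760 = 7,008, so the unrounded figures leave no slots. Against the rounded floors the slack is 5,856 − 5,800 = 56 in the new slots and 1,152 − 1,100 = 52 in the Year 3 repeat slots.

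**Step 3. One-year visits in Year 2.** One year at 80% use holds 0.8 × 10 × 5 × 48 = 1,920 people. I assume that use is even across years and that a one-year visit takes one screening slot, since it follows the initial-visit protocol. If a fraction r of Year 1 participants returns in Year 2:

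new screenings = 5,856 − 1,920r

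This falls below 5,800 once 1,920r exceeds 56, that is r above 56/1,920 = 2.9%. The protocol gives no value for r, so the rates below are assumptions. The maximum 95% margin is 1.96 × √(0.25/n). The use needed to keep 5,800 is 5,800/(7,320 − 2,400r), where 2,400 = 10 × 5 × 48 is one year at full use.

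| Assumed r | New screenings at 80% use | Maximum margin (points) | Use needed for 5,800 |
|---|---|---|---|
| 5% | 5,760 | 1.29 | 80.6% |
| 10% | 5,664 | 1.30 | 81.9% |
| 30% | 5,280 | 1.35 | 87.9% |
| 50% | 4,896 | 1.40 | 94.8% |

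At n = 5,800 the maximum margin is 1.29 points.

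**Step 4. The two-year figure.** To reach 1,100 two-year visits, 1,100/1,920 = 57% of Year 1 participants must return. At the same time, no more than 52 of the 1,152 Year 3 repeat visits may be one-year visits.

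**Step 5. When do Year 3 slots run out?** Suppose the one-year and two-year return rates are both r. Year 2 then enrols 1,920(1 − r) new people. Year 3 demand is 1,920r two-year visits plus 1,920r(1 − r) one-year visits, or 1,920r(2 − r). Setting this equal to 1,152 gives r(2 − r) = 0.6, so r = 1 − √0.4 = 37%.
- At r = 30%: 576 two-year plus 403 one-year visits = 979, which fits. The two-year cohort is 576 because of attendance.
- At r = 50%: 960 + 480 = 1,440, which exceeds 1,152. Slots are now the limit.

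**The case against.** **The Year 3 total does include one-year visits.** The repeat block is described as one- or two-year visits, and 432, 1,008 and 1,440 are labelled only as repeats or re-screenings. This stands. In Year 3 the fault is the two-year label in the closing clause. The outright omission is confined to the Year 2 slots counted as new.

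**80% is a cautious planning level, with 8,760 − 7,008 = 1,752 slots above it.** A reader might infer that the targets are impossible. The documents do not support that: 5,800 can be kept at about 82% use with 10% return, or 88% with 30%. But the protocol gives both figures at 80%, so drawing on the reserve changes the stated assumption.

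**The two-year loss depends on an attendance rate nobody has stated.** A reader might subtract one-year visits from 1,152 and report the remainder as the shrunken two-year cohort. That pairs a low one-year return with a two-year return of about 57%. The protocol states neither rate. With equal rates, Year 3 slots do not bind below about 37%, so that loss cannot be claimed from the documents.

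**No number of one-year visits is promised, and little inference rests on the figures.** Participants are only encouraged to return, enrolment is given as approximate, and the two-year outcomes are secondary. This limits the importance of the point. It does not make the stated sizes follow from the stated allocation.

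**Conclusion.** The concern holds as an inconsistency between the slot descriptions and the stated sizes. At 80% use, 5,856 new and 1,152 repeat visits take up all 7,008 slots. The 56 + 52 = 108 slots that appear against the rounded targets are a rounding residue and should not be read as capacity reserved for one-year visits.

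For new screenings, the total falls below 5,800 once one-year return in Year 2 passes 2.9%. It reaches 5,664 at an assumed 10% and 5,280 at 30%. The cost in prevalence precision is small, at most 0.06 points of margin over that range (1.29 to 1.35). The matter is mainly the target for a primary outcome that is itself a count.

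The two-year figure holds only with about 57% two-year return and almost no one-year visits in Year 3. Whether slots or attendance would limit that cohort cannot be settled without stated return rates.

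These results assume even use across years and one slot per one-year visit. The return rates are illustrative.

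**What to change.** In the Sample Size paragraph:

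1. Take one-year visits out of the Year 2 new slots, using a stated assumed return rate.
2. Relabel the 1,152 as one-year and two-year re-screens combined.
3. Give the two-year number separately, with its own assumed return rate.
4. Either restate the new-screening number at 80% use and carry the revised n and margin into Specific Aim 2 and the Aim 2 Data Analysis, or state the higher use needed to keep 5,800, in which case those two places can keep that n.

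The cost is wording only, with no added enrolment or visits. The downside is a slightly less favourable stated size and a smaller stated two-year cohort.

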**Post Program Participant Interview:** We will ask up to 75 participants to participate in a post program interview to identify program components that are helpful/unhelpful and areas for improvement. We will randomly contact English speaking participants within our study database that agreed to be contacted for future studies. The study consent document contains an additional signature section for participants to consent/not consent contact for future research. Selected participants will be contacted by phone, or in-person following their last appointment. Interviewers will follow the survey interview guide. Interviews will be conducted via in-person at the clinics, telephone, or UM Zoom. Participants will receive a \$20.00 Visa Gift Card or check by mail or in-person. Additionally, interviews will be recorded, transcribed, and stored on a secure UM server. Qualitative software such as Dedoose may be utilized. 1/24/2023 English post program interviews have been completed.

**Evaluation of "No-show" Appointments:** We will evaluate our high (approximately 35%) no-show and last-minute cancelations rates at this community clinic study (Hope & Hamilton

Community Clinic). The SIGHT study is open to non- clinic patients, therefore, potential participants may or may not be clinic patients. We will only review data of the SIGHT study "no shows" and will not include the clinics appointment "no shows". When potential participants contact the SIGHT team, the team member reviews the recruitment script that describes the study. Following this discussion and verification of study eligibility, a medical record number (MRN) in MiChart is created for those that do not already have an MRN. The SIGHT study baseline appointment is then made within the MiChart system. This process is completed prior to consent.

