#### **Data Analysis**

Primary Outcome Analysis: The primary outcomes will be the number of participants screened, the prevalence of glaucoma/glaucoma suspect diagnosis and the cost per case of detected disease. related macular degeneration) will be summarized similarly. Based on the anticipated sample size (n=5800), the margin of error is at most 1.2 percentage points for the overall prevalence (but could be larger for annual and by-site estimates).

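### The target of 5,800 new screenings assumes 80% slot use and is not reconciled with the study's own missed-appointment rate of about 35%; without refill or overbooking, that rate gives about 4,760

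*Protocol*

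**What the plan says.** The Aim 2 Sample Size paragraph builds the screening target from technician slots. Its daily load is "A typical day for each technician will include 5 screenings and 5 one-month follow-up visits". For the first two years it says "In the first 2 years (48 weeks each) at each site, all screenings will be of new or 1 year follow up patients", and for the third "year, 2 will be new and 3 will be one or two-year re-screening visits". It then gives capacity by site, for example "At Hope, the technician has capacity for 2448 new screenings and 432 repeat screenings in 4 years", and adds the sites: "Thus full capacity is 7320 new screenings and 1440 re-screenings". The target follows from one further assumption: "Operating at just 80% capacity enrolls over 5,800 patients for new screenings including over 1100 with 2-year re-screenings".

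The figure of about 5,800 also stands in the Specific Aim/Hypothesis section (Aim 2). The Aim 2 Primary Outcome Analysis uses it as the basis for its precision statement: "the margin of error is at most 1.2 percentage points for the overall prevalence".

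The paragraph on evaluating no-show appointments says: "We will evaluate our high (approximately 35%) no-show and last-minute cancelations rates at this community clinic study". It limits that evaluation to missed study appointments, leaving out the clinics' other appointments, and it describes how the baseline appointment is booked before consent.

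The Recruitment section says that technicians with free time will encourage referral of diabetic patients who are in clinic that day, and that self-referrals are accepted. It gives no figure for how many open slots this would fill.

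**The concern.** Using 80% of slots means losing 20% of them. The same protocol puts missed study appointments at about 35% and calls that rate high. The visit described alongside the rate, the baseline appointment, is the visit that the Sample Size paragraph counts as a new screening. The Sample Size paragraph does not mention missed appointments, and the no-show paragraph does not mention the target.

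The count of people screened is itself one of the Aim 2 primary outcomes, and 5,800 is the number against which it will be read. The same number carries the stated precision of the prevalence estimate. If 80% use is out of reach at the study's own attendance, both are overstated.

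**Working it through.** **Inputs.** From Sample Size: 5 screening slots per technician-day; 48 weeks per year; Hope 3 technician-days a week for 4 years; Hamilton 5 + 2 = 7 technician-days a week for 3.5 years; 3 of 5 slots in year 3 for re-screening; 80% use. From the no-show paragraph: about 35% of appointments missed or cancelled late. From Primary Outcome Analysis: n = 5,800 and a margin of at most 1.2 points.

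**Step 1: reproduce the plan's figures.**
- Hope: 3 × 5 × 48 = 720 slots a year; over 4 years 2,880. Year-3 re-screening: 720 × 3/5 = 432. New: 2,880 − 432 = 2,448.
- Hamilton: 7 × 5 × 48 = 1,680 slots a year; over 3.5 years 5,880. Year-3 re-screening: 1,680 × 3/5 = 1,008. New: 5,880 − 1,008 = 4,872.
- Totals: 2,448 + 4,872 = 7,320 new; 432 + 1,008 = 1,440 repeat.
- At 80%: 7,320 × 0.80 = 5,856 and 1,440 × 0.80 = 1,152.

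Every stated figure reproduces, so the arithmetic of the paragraph is sound. The question is only whether 80% is compatible with the reported attendance.

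**Step 2: apply the 35%.** Let f be the share of missed slots that are refilled, with each slot booked once. Use = 0.65 + 0.35f. The protocol does not give f, so it is shown as a range. The re-screening column assumes that the 35% applies to those visits as well.

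| f | Use | New screenings | Re-screenings (assumed same rate) |
|---|---|---|---|
| 0% | 65% | 4,758 | 936 |
| 25% | 73.75% | 5,399 | 1,062 |
| 43% | 80% | 5,856 | 1,152 |
| 50% | 82.5% | 6,039 | 1,188 |

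Shortfall at f = 0: 5,800 − 4,758 = 1,042 (18%) for new screenings; 1,100 − 936 = 164 (15%) for re-screenings.

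**Step 3: what the stated targets require.**
- Refill for 5,800: (5,800/7,320 − 0.65)/0.35 = 0.41.
- Refill for 1,100: (1,100/1,440 − 0.65)/0.35 = 0.33.
- Overbooking for 5,800 with no refill: 5,800/0.65 = 8,923 bookings; 8,923/7,320 = 1.22, that is about 22%.

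**Step 4: precision.** Worst-case 95% margin = 1.96 × √(0.25/n).
- n = 5,800: 1.29 points.
- n = 4,758: 1.42 points.
- Difference due to attendance: 1.42 − 1.29 = 0.13 points.

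The Background section reports glaucoma plus suspect rates of 17% + 21% = 38% and 19% + 23% = 42% in two community programmes. At those prevalences the margin is 1.25 to 1.27 points at n = 5,800 and 1.38 to 1.40 at n = 4,758.

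**The case against.** A reader might infer that a 35% missed-appointment rate caps the study at about 4,750 new screenings and 940 re-screenings, and that it moves the margin from 1.2 to 1.4 points. The documents do not support that, for three reasons.

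First, a no-show rate is missed bookings over bookings, whereas capacity use is screenings done over slots. The two are complements only if every slot is booked exactly once and no missed slot is refilled. The protocol says neither. It plans same-day referrals into free technician time and takes self-referrals, and a protocol need not set out its overbooking practice. So 4,758 is one end of a range. This stands in full.

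Second, the 35% is described with baseline appointments of people not yet enrolled. Nothing shows that it holds for enrolled participants called back for re-screening, and no denominator or period is given. The 936 therefore rests on an added assumption. This also stands. The result for new screenings does not depend on it.

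Third, most of the gap between 1.2 and 1.4 points has nothing to do with attendance on its own: the worst-case margin is already 1.29 at n = 5,800. That the stated maximum of 1.2 is exceeded at the planned size is a separate point.

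It can also be said that 80% was a planning figure, that the 35% reads as experience from the running study, and that missing a projection does not bias a descriptive prevalence estimate. That limits the harm, but it does not reconcile the two figures. Same-day referral is also a limited remedy: it is aimed at diabetic patients who happen to be in clinic, for an examination of about an hour, and it cannot readily fill a re-screening slot, which needs someone screened one or two years before.

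**Conclusion.** The point holds as an unreconciled planning assumption, not as an arithmetic error. The protocol's own attendance figure supports 5,800 new screenings only if about 41% of missed slots are refilled, or slots are overbooked by about 22%, and neither level is stated. With no refill the figure is 4,758, or 18% lower; with 25% refill it is about 5,400. This rests on the 35% applying to baseline screening slots across the programme.

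For re-screening, the no-refill figure of 936 against 1,100, and the 33% refill needed to close the gap, hold only if the same rate is assumed for those visits.

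The consequence for precision is minor, about 0.13 points in the worst case, and would not change how the prevalence is read. The consequence for the count of people screened, a primary outcome, is the larger one.

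**What to change.** In the Specific Aim/Hypothesis section (Aim 2), the Sample Size paragraph and the Aim 2 Primary Outcome Analysis, replace the single figure with a range tied to the reported attendance:

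- New screenings: about 4,750 with no refill, up to 5,800 with about 41% of missed slots refilled (or about 22% overbooking). If 5,800 is kept as the target, state the refill or overbooking level on which it depends.
- Re-screenings: about 940 to 1,100, labelled as assuming that the baseline missed-appointment rate also applies to these visits.
- Worst-case 95% margin: about 1.3 points (n = 5,800) to 1.4 points (n = 4,758).

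Add the denominator and period behind the 35%, and the slot use achieved so far if it is known, since that would narrow the range directly. The change is to wording only; its cost is that the stated size and precision look slightly less favourable.
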